## 10. STUDY MANAGEMENT BY ASTRAZENECA REPRESENTATIVE

### 10.1 Training of site personnel

Before the first patient is entered into the study, an AstraZeneca representative will review and discuss the requirements of the study protocol and related documents with the site personnel and also train them in any protocol-specific procedures.

The investigator will ensure that appropriate training relevant to the study is given to all investigational staff involved in the study.

The investigator will also maintain a record of all individuals involved in the study (medical, nursing, and other staff).

## **10.2 Monitoring of the study**

During the study, an AZ representative will have regular contacts with the study site, including visits, as per local regulations, to verify the conduct of the study.

The AZ representative will be available during the course of the study if the investigator or other staff at the site needs information and advice about the study conduct.

### **10.2.1 Source data**

Study sites will maintain source data in accordance with Good Clinical Practice (GCP) or local regulations.

### **10.2.2 Study agreements**

The site and the investigator at each site must comply with all the terms, conditions, and obligations of the Study Agreement, or equivalent, for this study. In the event of any inconsistency between this study protocol and the Study Agreement, the terms of the protocol shall prevail with respect to the conduct of the study and the treatment of patients and in all other respects, not relating to study conduct or treatment of patients, the terms of the Study Agreement shall prevail.

Agreements between AstraZeneca (or its delegation) and the investigator/site must be in place before any study-related procedures can take place.

### **10.2.3 Archiving of study documents**

The Investigator must follow the archiving requirements outlined in the Study Agreement.

### **10.2.4 Timetable and End of Study**

The study is expected to start in Q3 2015 and to end by Q2 2020.

The study will be closed in each participating country as soon as possible following national reimbursement of AZD9291 in that country (up to a max of 90 days post reimbursement). Enrolment will be closed within 6 months after market license approval in that country or at national reimbursement, whichever is sooner.

Patients withdrawing from the treatment prior to national reimbursement will be followed up as part of this study.

At national reimbursement, patients still on treatment will be transitioned to commercial supply as long as patient is benefitting from treatment as per investigator assessment and in accordance with national regulations in the countries where the study is conducted. Once the study is closed no further data will be collected.

In the event that national reimbursement should not be granted following a reasonable time after market license approval in the country, the study will be closed in a maximum period of 18 months after the last patient is enrolled in that country. Contingencies will be made locally to ensure continued drug supply for patients who are still deriving benefit from AZD9291 at that time.

The end of the study is defined as ‘the last visit of the last subject undergoing the study’.

AstraZeneca may also terminate the entire study prematurely if concerns for safety arise within this study or in any other study with AZD9291.

## **11. ETHICAL AND REGULATORY REQUIREMENTS**

### **11.1 Ethical conduct of the study**

The study will be performed in accordance with ethical principles that have their origin in the Declaration of Helsinki and are consistent with International Conference on Harmonization (ICH)/Good Clinical Practice (GCP), applicable regulatory requirements and the AstraZeneca policy on Bioethics and Human Biological Samples.

### **11.2 Patient data protection**

The Informed Consent Form (ICF) will incorporate (or, in some cases, be accompanied by a separate document incorporating) wording that complies with relevant data protection and privacy legislation.

AstraZeneca or its representative will not provide patient information to patients, any insurance company, any employer, their family members, general physician or to any other third party, unless required to do so by law.

Precautions are taken to preserve confidentiality and prevent data being linked to the identity of the patient. Also Regulatory authorities may require access to the relevant files.

### **11.3 Ethics and regulatory review**

An Independent Review Board (IRB)/Ethics Committee (EC) must approve the final study protocol, including the final version of the ICF and any other written information and/or materials to be provided to the patients, as per local regulations. The opinion of the IRB/EC must be given in writing.

AstraZeneca or its representative must approve any modifications to the ICF that are needed to meet local requirements.

If required by local regulations, the protocol must be re-approved by the IRB/EC annually.

Before enrollment of any patient into the study, the final protocol, including the final version of the ICF, is to be approved by the national regulatory authority or a notification to the national regulatory authority is to be done, according to local regulations.

AstraZeneca or its representative will provide Regulatory Authorities, IRB/EC, and investigators with safety updates/reports according to local requirements.

Each investigator is responsible for providing the IRB/EC with reports of any serious and unexpected adverse drug reactions from any other study conducted with the IP. AstraZeneca or its representative will provide this information to the investigator so that he/she can meet these reporting requirements.

#### **11.4 Informed consent**

The investigator at each site will:

- Ensure each patient is given full and adequate oral and written information about the nature, purpose, possible risk, and benefit of the study.
- Ensure each patient is notified that they are free to discontinue from the study at any time.
- Ensure that each patient is given the opportunity to ask questions and allowed time to consider the information provided.
- Ensure each patient or legally acceptable representative provides signed and dated ICF before conducting any procedure specifically for the study.
- Ensure the original, signed ICF(s) is/are stored in the investigator's study file.
- Ensure a copy of the signed ICF is given to the patient.
- Ensure that any incentives for patients who participate in the study as well as any provisions for patients harmed as a consequence of study participation are described in the informed consent form that is approved by an IRB/EC.
- Ensure that the Addendum to the ICF is signed and dated for the subset of patients tested for a T790M positive mutation via the **cobas®** EGFR Mutation Test (or any other molecular testing methods if relevant) before any imaging assessments are collected.

#### **11.5 Changes to the protocol and informed consent form**

If there are any substantial changes to the study protocol, then these changes will be documented in a new version of the study protocol (Revised Study Protocol).

The amendment in the form of a revised protocol is to be approved by the relevant IRB/EC and if applicable, the national regulatory authority needs also to be notified or has to provide approval, before implementation. Local requirements are to be followed for revised protocols.

AstraZeneca or its representative will distribute any new versions of the protocol to each participating investigator. For distribution to IRB/EC, see Section [11.3](#).

If a protocol amendment requires a change to a site's ICF, AstraZeneca (or its representative) and the site's IRB/EC are to approve the revised ICF before the revised form is used.

If required by local regulations, any administrative change will be communicated to or approved by each IRB/EC.

## **11.6 Audits and inspections**

Authorized representatives of AstraZeneca, a regulatory authority, or an IRB/EC may perform audits or inspections at the study site, including source data verification. The purpose of an audit or inspection is to systematically and independently examine all study-related activities and documents, to determine whether these activities were conducted, and data were recorded, analyzed, and accurately reported according to the protocol, GCP, ICH guidelines, and any applicable regulatory requirements. The investigator will contact AstraZeneca immediately if contacted by a regulatory agency about an inspection at the study site.

## **Appendix A Additional Safety Information**

### **Further Guidance on the Definition of a Serious Adverse Event (SAE)**

#### **Life threatening**

‘Life-threatening’ means that the subject was at immediate risk of death from the AE as it occurred or it is suspected that use or continued use of the product would result in the subject’s death. ‘Life-threatening’ does not mean that had an AE occurred in a more severe form it might have caused death (eg, hepatitis that resolved without hepatic failure).

#### **Hospitalisation**

Outpatient treatment in an emergency room is not in itself a serious AE, although the reasons for it may be (eg, bronchospasm, laryngeal oedema). Hospital admissions and/or surgical operations planned before or during a study are not considered AEs if the illness or disease existed before the subject was enrolled in the study, provided that it did not deteriorate in an unexpected way during the study.

#### **Important medical event or medical intervention**

Medical and scientific judgement should be exercised in deciding whether a case is serious in situations where important medical events may not be immediately life threatening or result in death, hospitalisation, disability or incapacity but may jeopardize the subject or may require medical intervention to prevent one or more outcomes listed in the definition of serious. These should usually be considered as serious.

Simply stopping the suspect drug does not mean that it is an important medical event; medical judgement must be used.

- Angioedema not severe enough to require intubation but requiring iv hydrocortisone treatment
- Hepatotoxicity caused by paracetamol (acetaminophen) overdose requiring treatment with N-acetylcysteine
- Intensive treatment in an emergency room or at home for allergic bronchospasm
- Blood dyscrasias (eg, neutropenia or anaemia requiring blood transfusion, etc) or convulsions that do not result in hospitalisation

Development of drug dependency or drug abuse

#### **A Guide to Interpreting the Causality Question**

When making an assessment of causality consider the following factors when deciding if there is a ‘reasonable possibility’ that an AE may have been caused by the drug.

- Time Course. Exposure to suspect drug. Has the subject actually received the suspect drug? Did the AE occur in a reasonable temporal relationship to the administration of the suspect drug?
- Consistency with known drug profile. Was the AE consistent with the previous knowledge of the suspect drug (pharmacology and toxicology) or drugs of the same pharmacological class? Or could the AE be anticipated from its pharmacological properties?
- De-challenge experience. Did the AE resolve or improve on stopping or reducing the dose of the suspect drug?
- No alternative cause. The AE cannot be reasonably explained by another aetiology such as the underlying disease, other drugs, other host or environmental factors.
- Re-challenge experience. Did the AE reoccur if the suspected drug was reintroduced after having been stopped? AstraZeneca would not normally recommend or support a re-challenge.
- Laboratory tests. A specific laboratory investigation (if performed) has confirmed the relationship.

In difficult cases, other factors could be considered such as:

- Is this a recognized feature of overdose of the drug?
- Is there a known mechanism?

Causality of 'related' is made if following a review of the relevant data, there is evidence for a 'reasonable possibility' of a causal relationship for the individual case. The expression 'reasonable possibility' of a causal relationship is meant to convey, in general, that there are facts (evidence) or arguments to suggest a causal relationship.

The causality assessment is performed based on the available data including enough information to make an informed judgment. With limited or insufficient information in the case, it is likely that the event(s) will be assessed as 'not related'.

Causal relationship in cases where the disease under study has deteriorated due to lack of effect should be classified as no reasonable possibility.

## Appendix B Guidance regarding Potential Interactions with Concomitant Medications

The use of any natural/herbal products or other “folk remedies” should be discouraged, but use of these products, as well as use of all vitamins, nutritional supplements, and all other relevant concomitant medications must be recorded in the eCRF.

### Drugs inducing cyp3a4 metabolism that AstraZeneca strongly recommend are not combined with azd9291

AZD9291 is metabolised by CYP3A4 and CYP3A5 enzymes.

A drug-drug interaction study of AZD9291 evaluated in patients showed that there is potential for AZD9291 being a victim when co-administered with strong inducers of CYP3A4 (AZD9291 concentrations are decreased when co-dosed with rifampicin).

The following potent inducers of CYP3A4 must not be used during this study for any patient receiving AZD9291.

**Table 6 Drugs inducing CYP3A4**

Contraindicated drugs	Withdrawal period prior to AZD9291 start
Carbamazepine, phenobarbital, phenytoin, rifampicin, rifabutin, rifapentin St John’s Wort	3 weeks
Phenobarbitone	5 weeks

This list is not intended to be exhaustive, and a similar restriction will apply to other agents that are known to strongly modulate CYP3A4 activity. Appropriate medical judgment is required. Please contact AstraZeneca with any queries you have on this issue.

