### 3.2 Exclusion criteria

Patients will not be enrolled in this study if any of the following exclusion criteria are met:

1. Previous (within 6 months) or current treatment with AZD9291
2. Patients currently receiving (or unable to stop use at least 1 week prior to receiving the first dose of AZD9291) any treatment known to be potent inhibitors or inducers of cytochrome P450 (CYP) 3A4 (Appendix B)
3. Any evidence of severe or uncontrolled systemic diseases, including uncontrolled hypertension, active bleeding diatheses, active infection\* including hepatitis B, hepatitis C and human immunodeficiency virus, or significantly impaired bone marrow reserve or organ function, including hepatic and renal impairment, which in the investigator's opinion would significantly alter the risk/benefit balance.

\* active infection will include any patients receiving intravenous treatment for any infection and patients with hepatitis B or C surface antigen (+) – Patients receiving oral antiviral suppressive therapy for hepatitis B or C will be permitted to enrol in the study.

4. Patient with symptomatic central nervous system (CNS) metastases who is neurologically unstable or has required increasing doses of steroids to manage CNS symptoms within the 2 weeks prior to start AZD9291 administration
5. Past medical history of ILD, drug-induced ILD, radiation pneumonitis requiring steroid treatment, or any evidence of clinically active ILD
6. Any of the following cardiac criteria:

- a. Mean resting corrected QT interval (QTcF) > 470 ms using Fredericia's formula :

$$QT_{cF} = \frac{QT}{\sqrt[3]{RR}}$$

- b. Any clinically important abnormalities in rhythm, conduction or morphology of resting ECG (e.g., complete left bundle branch block, third degree heart block, second degree heart block)
- c. Any factors that increase the risk of QTc prolongation or risk of arrhythmic events

7. Any unresolved toxicity from prior therapy CTCAE  $\geq$  grade 3 at the time of starting treatment
8. History of hypersensitivity to excipients of AZD9291 or to drugs with a similar chemical structure or class to AZD9291

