period (30 days post-last dose). Patients taking concomitant medications whose disposition is dependent upon CYP3A4 and breast cancer resistance protein and which have a narrow therapeutic index should be closely monitored for signs of changed tolerability as a result of increased exposure of the concomitant medication whilst receiving AZD9291. Patients taking concomitant medications whose disposition is dependent upon CYP3A4, CYP1A2, CYP2C or p-glycoprotein and which have a narrow therapeutic index should be closely monitored for reduction in therapeutic activity as a result of the reduced exposure of the concomitant medication while receiving AZD9291. Guidance on medications to avoid, medications that require close monitoring and on washout periods is provided (see [Appendix B](#)).

Up to 3-fold increase in exposure may occur in statin exposure when co-administered with AZD9291. It is recommended that the starting and maintenance dose of statins should be as low as possible and should be guided by the statin prescribing information.

Patients taking warfarin should be monitored regularly for changes in prothrombin time or international normalized ratio.

Patients who wear contact lenses must discontinue wearing their lenses if they have any mild to moderate eye symptoms (CTCAE grade  $\leq 2$ ) while receiving treatment with AZD9291 until at least one week after symptoms have resolved. If a patient has a recurrence of eye symptoms or experiences any severe (CTCAE grade  $\geq 3$ ) ocular events, they must discontinue wearing their contact lenses until at least one week after treatment with AZD9291 is permanently discontinued. Patients must not use any eye drops or ointment for treatment of eye symptoms, unless agreed to by a study doctor, at any time during the study until 1 week after AZD9291 has been permanently discontinued. Patients must consult their investigator promptly if they have any concerns.

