# **9. STATISTICAL ANALYSES**

Statistical analysis and generation of all tables, listings and figures will be performed by using SAS® (SAS Institute, North Carolina), version 9.2 or higher.

The analyses of the data collected within this study will be descriptive only.

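### Appendix B Table 6 lists one drug under two names with two withdrawal periods, 3 and 5 weeks, and exclusion criterion 2 gives a third

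*Protocol*

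**What the plan says.** Appendix B introduces Table 6 with the sentence "The following potent inducers of CYP3A4 must not be used during this study for any patient receiving AZD9291". The table's second column is headed "Withdrawal period prior to AZD9291 start", and there are two rows. The first lists "Carbamazepine, phenobarbital, phenytoin, rifampicin, rifabutin, rifapentin" together with St John's Wort, at 3 weeks. The second lists "Phenobarbitone" alone, at 5 weeks.

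Two places in the body of the protocol send sites to this appendix. Section 4.2 (Restrictions) says "Guidance on medications to avoid, medications that require close monitoring and on washout periods is provided" and refers to Appendix B. Exclusion criterion 2 in section 3.2 excludes patients who are taking a potent CYP3A4 inhibitor or inducer, or who are "unable to stop use at least 1 week prior to receiving the first dose of AZD9291", and it also cites Appendix B. Section 3 allows no exceptions to the eligibility criteria.

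A note under Table 6 says that the list is not complete, calls for medical judgement and invites queries to the sponsor.

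**The concern.** A washout table should give one answer per drug. Here the answer depends on which name the site uses. The study is multinational, and a site that knows the drug by one name will find that name, read the period beside it and have no reason to look further. Two sites could treat identical patients differently while each believes it has followed the protocol.

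The conflict lies inside Table 6. Exclusion criterion 2 adds a third figure, but replacing that figure with a pointer to Table 6 would not solve the problem, because the table would still return two periods for this drug. What is at stake is consistent application of a patient-level entry rule across sites.

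**Working it through.** No sample size, power or error-rate calculation applies. The withdrawal periods are stated rules, not derived figures, and section 9 of the protocol says "The analyses of the data collected within this study will be descriptive only". The check is to set the three rules side by side and convert them to days.

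Inputs:
- Table 6, row with phenobarbital: 3 weeks × 7 = 21 days.
- Table 6, row with phenobarbitone: 5 weeks × 7 = 35 days.
- Exclusion criterion 2, period stated in the criterion: 1 week × 7 = 7 days.

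Gap between the two rows: 35 − 21 = 14 days.

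Classification by days between stopping the drug and the first AZD9291 dose:

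| Days off the drug | Exclusion 2 (7 days) | Row at 3 weeks (21 days) | Row at 5 weeks (35 days) |
|---|---|---|---|
| 0 to 6 | not met | not met | not met |
| 7 to 20 | met | not met | not met |
| 21 to 34 | met | met | not met |
| 35 or more | met | met | met |

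The two rows of Table 6 disagree only in the third band, 21 to 34 days. Below 21 days both reject the patient, and from 35 days both accept. The period written in exclusion criterion 2 disagrees with at least one row from day 7 to day 34, and with both rows from day 7 to day 20.

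Nothing in Appendix B distinguishes the two names by salt, dose, route or indication, so the rows cannot be read as covering different products. In the text each row carries its own period, so a broken table is not a likely explanation. The table is current protocol text, not part of the version history.

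**The case against.** The strongest reply is that the appendix is guidance, that it calls for judgement, and that it gives sites a route to ask. This is fair in part: a site that notices the conflict can resolve it. But the route helps only a site that notices. The call for judgement follows the remark that other, unlisted agents fall under a similar restriction, and it does not choose between two periods stated for a listed drug.

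A second reply is that exclusion criterion 2 is the binding rule, and a patient 21 to 34 days off the drug satisfies its one-week figure. The criterion cites Appendix B without saying whether it takes in the withdrawal periods or only the list of drugs. That ambiguity belongs to the same defect and does not answer it.

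Three stronger readings are tempting, and the documents do not support them.

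- *A count of affected patients.* The documents give none. If one assumed that 0.2% to 2% of about 3500 patients stop this drug before entry, that would be 0.002 × 3500 = 7 to 0.02 × 3500 = 70 patients. That prevalence has no source in the documents. Even if it were right, the figure would be a ceiling for the conflict inside Table 6, because only those who stopped 21 to 34 days before the first dose are classified differently by the two rows.
- *Reduced early exposure to AZD9291.* Appendix B reports lower AZD9291 concentrations when the drug is given together with rifampicin. It says nothing about residual induction in a patient already off the inducer for three weeks or more.
- *Irreproducible deviation review.* SAP section 2.2 names eligibility and prohibited-medication categories, but its examples include no check of Table 6 washout periods. The detailed rules sit in a separate deviation specification that is not among the documents. How a 21-to-34-day case would be classified cannot be established from what is available.

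**Conclusion.** The point holds: Table 6 is wrong as written, and the severity is low. One substance has two withdrawal periods 14 days apart, patients who stopped it 21 to 34 days before the first dose meet one row and fail the other, and exclusion criterion 2 states a third period while citing the same appendix.

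The conclusion rests on two assumptions: that phenobarbital and phenobarbitone are the same substance, which the protocol does not state but which is ordinary drug nomenclature; and that the published table has the two rows as they read in the text.

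A reader might infer that the study's results are at risk. The documents do not support that. The full analysis set is every patient who received at least one dose, so a washout discrepancy removes nobody from it, and nothing ties this entry to the overall survival precision table or the efficacy estimates. The number of patients concerned is unknown and probably small. The defect is one of consistent conduct across sites.

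**What to change.** Merge the two rows for this substance into one entry that shows both names and a single withdrawal period. The sponsor should decide the period; this review takes no view on whether 3 weeks, 5 weeks or another figure is right.

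In the same edit, reconcile exclusion criterion 2 with Table 6, and say explicitly whether its reference to Appendix B brings in the withdrawal periods or only the list of drugs. Use the agreed period wherever washout compliance is checked, including the deviation specification if it contains such a check.

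The cost is one table entry and a clarification to one criterion, which can go into the next protocol revision, with a letter to sites if earlier notice is wanted. No change to the analysis is needed.
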